1.7 I1. Institutional Review Board

The study protocol, informed consent form, study questionnaires and recruitment materials must be approved by the UCSF Committee on Human Research (CHR) prior to the start of the study. Protocol amendments generated during the study must be approved by the CHR prior to their implementation. The Sponsor-Institution (UCSF) and Investigator ([name]) shall be

responsible for reporting any serious adverse events associated with the use of the study drug to the ASMA (e-mail [contact] or fax to [contact]) and to the UCSF CHR.

I2. Informed Consent Form

Before individuals may participate in any screening procedures, informed consent for all phases of the trial must be obtained. The consent form will explain in lay language the goals of the study, the visits and procedures and the risks and benefits of participating. Any amendment to the protocol generated during the study that impacts participants will be reflected in a revised consent form that must be signed again by the participant.

K. SAMPLE SIZE JUSTIFICATION

Sample sizes between 24 and 50 have been recommended for feasibility/pilot studies.³²⁻³⁵ We plan to study up to 50 women with approximately 25 randomized to Mirabegron and 25 to a standard anticholinergic therapy (Detrol LA). One of the goals of this study is to estimate the standard deviation of the neuropsychologic battery scores as well as the potential effect size of Mirabegron against its comparator. These estimates will be used to develop sample size estimates for a larger clinical trial, if indicated. Thus, power analyses based on a sample size of 50 were not done for this proposal.

L. STATISTICAL CONSIDERATIONS

SA 1: We will observe the number of weeks required to enroll 50 participants into this pilot study, track the success rate of various recruitment approaches, track the numbers of women who are screened, found eligible, enrolled/randomized, and lost to follow-up, as well as those to terminate the study or discontinue study medication early, and calculate the cost of recruitment per participant.

SA 2: Analysis of covariance (ANCOVA) will be used to estimate the preliminary performance differences on and calculate the standard deviation of cognitive test scores and physical function and mobility test scores between the Mirabegron and standard anticholinergic therapy groups at week 8, controlling for baseline.

SA 3: Standard chi-square tests will be used to determine differences in report of adverse events at week 8.

SA 4: Number and proportion of participants reporting much better, somewhat better, about the same, somewhat worse and much worse memory and thinking since study enrollment will be calculated. Chi-square test for trend will be used to determine differences patient perception of cognitive change at week 8.

SA 5: ANCOVA will be used to estimate the preliminary differences and calculate the standard deviation of change in incontinence episode frequency measured on the 3-day diary between the Mirabegron and standard anticholinergic therapy groups at week 8, controlling for baseline.

M. NONADHERENCE, STUDY DRUG DISCONTINUATION AND EARLY STUDY DISCONTINUATION

All participants will be encouraged to take all doses of study medication unless safety is a concern. Study coordinators will ascertain reasons for nonadherence to study medication and attempt to help participants find ways to improve adherence. However, participants who are nonadherent with study medication will be urged to attend all study visits and complete all study measurements as planned. Adherence with study medication will be measured by tablet counts at each clinic visit.

Study drug will be discontinued in any participant who has any serious adverse event that, in the judgment of the clinical site investigator, is possibly related to treatment with study medication. Study medication may be resumed if, in the opinion of the clinical site investigator, the abnormal symptom, physical finding or test has been satisfactorily evaluated and found to be benign.

Participants will be considered to have permanently discontinued study medication if they report not taking study medication for 4 weeks or longer. In this case, study termination measurements will be obtained if possible.

All participants will be urged to attend all study visits and complete all study measurements as planned. However, participants can discontinue participation in the study at any time. Participants who miss a visit will be contacted by the study coordinator to reschedule the visit and to provide assistance in completing the visit. Participants who state that they no longer desire to participate in the trial will undergo study termination measurements if possible.

N. REFERENCES

1. Mitteness LS. The management of urinary incontinence by community-living elderly. *Gerontologist* 1987;27:185-93.

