The daily voiding diary period is defined as follows: "Awake Time" begins from the time the subject starts her day (time arose) until she goes to bed for that day. "Bed Time" is defined as the time the subject went to bed until she awoke to start the next day.

E5. Evaluation Schedule

Time of Visit	Tele-phone	SV	Base line	2wk phone	4wk	8wk	ET
Telephone Screening	X						
Information & Informed Consent		X					
3-day voiding diary Instruction		X					
Demographics		X					
Alcohol and Tobacco Use		X					
Medical History		X					
Mini-Mental Status Exam (MMSE)*		X					
Geriatric Depression Scale (GDS)*		X					
Concomitant Medication		X					
Dipstick urinalysis		X				X	X
PVR assessment		X				X	X
Voiding diary Review			X		X	X	X
Height^ and Weight			X			X	
Vital Signs		X	X		X	X	X
Health and Medications Update			X	X	X	X	X
Inclusion/Exclusion/Randomization			X				
Dispense study medication			X		X		
California Verbal Learning Test – Short Form (CVLT-SF)			X			X	X
Digit Span			X			X	X
Trail Making Test Parts A & B			X			X	X
Digit Symbol Substitution Task (DSST)			X			X	X
Pittsburgh sleep quality index (PSQI)			X			X	X
Epworth Sleepiness Scale (ESS)			X			X	X
Physical Function and Mobility: Short Physical Performance Battery (SPPB)			X			X	X
IADL			X			X	X
OAB-questionnaire			X			X	X
Patient Perception of Cognitive Change				X	X	X	X
Adverse events (self-report)				X	X	X	X

Patient Perception of Bladder Condition				X	X	X	X
Participant directed Dose Adjustment				X	X		
Assess study medication compliance				X	X	X	X
Trial medication return/count					X	X	X
Early Termination Report							X
Participant Satisfaction						X	X

[^] Height only at baseline visit

* The MMSE and the GDS will be used only as screening tests to determine eligibility, not as outcome measures

E6. Study Visits

The 8-week RCT requires 2 telephone visits (Telephone Screening, Week 2 Phone Call) and 4 in-clinic visits (Screening, Baseline, Week 4, Week 8 (or Early Termination) visit).

E6.1 Recruitment Phase

Women will be recruited by (1) direct, community-based efforts using large media (newspaper notices, television ads, etc.) and small media (brochures in local businesses, talks to local community, notices in churches, salons etc.); (2) seeking referrals from physician's offices (specifically in urology, urogynecology, gynecology, primary care, and geriatric medicine) and (3) purchasing targeted mailing lists.

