1.2 F3. Global Patient Perception of Cognitive Change

A single-item assessing patient's overall perception of their memory problems using a 5-point Likert scale, participants will be asked "Compared to 4 weeks ago, have you noticed that your memory and thinking are:" with responses of much better, somewhat better, about the same, somewhat worse, or much worse.

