1.4 F6. Physical Function and Mobility

Measured with Short Physical Performance Battery (SPPB) and Instrumental Activities of Daily Living (IADL) (same as used in the Health and Retirement Study). ²⁹ Clinically significant change includes new difficulty in I-ADL or worsening on the Short Physical Performance Battery (includes chair stand, balance, gait speed).²⁹

F7. Overactive Bladder Questionnaire (OAB-q)

OAB-q is a self-administered, 33-item, validated questionnaire that assesses how much the subject has been bothered by selected bladder symptoms during the previous week.³⁰ It consists of two distinct components. The first 8 questions comprise the symptom bother score. Questions 9-33 comprise the health-related quality of life (HRQOL) component, which includes the domains of coping, concern, sleep, and social interaction. Higher scores represent better quality of life. It will be administered at Baseline and Week 8 (or Early Termination) visits. Participants are not allowed to look at previously completed assessments.

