1.5 F8. Global Rating of Patient Satisfaction and Perceptions of Improvement

Two validated questions assessing patient's satisfaction with the intervention and perception of improvement of their bladder problems will be administered: ³¹

- Patient satisfaction question (PSQ): How satisfied are you with your progress in this program? With responses of Completely, Somewhat, or Not at all
- Global perception of improvement (GPI): Overall, do you feel that you are: Much Better, Better, About the same, Worse, or Much worse. This is compared to pre- intervention (so there is no baseline value).

F9. Other Measurements

Weight will be recorded in kilograms using a calibrated scale. Participants will be measured in light clothing (without shoes) to the nearest 0.5 kg. Standing height, which is measured at the baseline visit only, will be measured in centimeters with a calibrated wall-mounted Harpenden

stadiometer or ruler. Variables that may act as predictors of the frequency of incontinence will be documented at screening or baseline. These covariates include demographic characteristics (age, race/ethnicity, residency location (independent, assisted), relationship status, education), general health, genitourinary history (duration of incontinence, prior type and duration of therapy, amount of urine loss, pad use, drinking habits), smoking behavior, reproductive health (gravity, parity, route of delivery, menopause status, hormone therapy use), medical history/comorbidities (hypertension, cardiovascular disease, pulmonary disease, stroke, diabetes) surgical history (hysterectomy, pelvic organ prolapse repair, other pelvic or abdominal surgery), history of falling on past month, and medications.

G. DATA MANAGEMENT

G1. Data Collection

A secure study database will be developed using the UCSF Research Electronic Data Capture system (REDCap). REDCap enables researchers to create on-line databases for input, cleaning, management, and exporting of all study data. The study programmer analyst, who has previously used REDCap to create study databases for large multi-centered studies, will create a REDCap database unique to our study. REDCap also contains advanced features for data cleaning, importing, and embedded calculated database fields and is supported by the UCSF Information Technology Service.

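### SA3 ties the only between-arm adverse-event comparison to the report at Week 8, although self-reports are also scheduled at Week 2, Week 4 and Early Termination

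*Combined protocol and SAP*

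**What the plan says.** Section L, SA 3, contains the whole between-arm analysis of adverse events: "Standard chi-square tests will be used to determine differences in report of adverse events at week 8". It does not define which reports count, over what period, or which women form the denominator.

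In the E5 schedule, the row that begins "Adverse events (self-report" is marked at the 2-week call, the 4-week visit, the 8-week visit and Early Termination (ET). The visit narratives in E6.5 do not name the adverse-event form, so its timing rests on that table. No recall period is given for it.

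E6 and the heading of E6.5c name Early Termination as the alternative to Week 8, and the sections on the diary (F1), the PSQI (F5) and the OAB-q (F7) do the same. E5 gives it a separate column. Section M says that "participants who are nonadherent with study medication will be urged to attend all study visits and complete all study measurements as planned"; for women who have been off drug for 4 weeks or who withdraw, termination measurements are taken where this can be done.

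Section C names dry mouth, constipation, vision and falling as examples of the events that SA3 is meant to compare.

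**The concern.** SA3 asks for preliminary between-arm data on events that may be brief or discrete. A fall reported at the Week 2 call need not be reported again at Week 8. Dry mouth reported at Week 4 may have gone by Week 8. If the comparison uses only the Week 8 report, such events are collected on treatment and then left out of the one analysis that compares the arms.

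The documents supply that comparison nowhere else. The safety monitor reviews adverse effects after 20 and 40 women complete the 4-week visit (section H), and SA1 tracks early stopping, but neither yields the SA3 estimate. With no counting rule, the choice between a Week 8 count and a cumulative count could also be made after the data are seen.

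A related weakness is the choice of test. With about 25 women per arm, an uncommon event gives expected counts too small for a plain chi-square test.

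**Working it through.** **Step 1: what the phrase means within section L.** SA2 and SA5 also place their analyses at week 8. For SA5 the E5 schedule has the diary reviewed at Week 4 as well, yet the outcome is the week 8 frequency adjusted for baseline, so there the phrase denotes the Week 8 measurement and not everything collected up to it. Applied to SA3, the same usage gives the Week 8 report alone. SA4 is less clear. It tabulates categories ending in "much worse memory and thinking since study enrollment will be calculated" and then states "Chi-square test for trend will be used to determine differences patient perception of cognitive change at week 8", but the item itself (F3) asks "Compared to 4 weeks ago, have you noticed that your memory and thinking are". SA4 therefore does not establish that the phrase is cumulative.

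**Step 2: which reports are scheduled and which are named.**

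| Report | Scheduled in E5 | Named in SA3 |
|---|---|---|
| Week 2 | yes | no |
| Week 4 | yes | no |
| Week 8 | yes | yes |
| Early Termination | yes | no (paired with Week 8 in the visit text only) |

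**Step 3: how much it could matter.** The plan states no adverse-event rate, so there is no figure to reproduce. All counts below are assumptions, with 25 per arm taken from section K. The first count is tolterodine, the second mirabegron.

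Risk difference: d = p1 − p2. The 95% interval is Newcombe's, built from the Wilson limits (l, u) of each proportion: lower = d − √[(p1 − l1)² + (u2 − p2)²], upper = d + √[(u1 − p1)² + (p2 − l2)²].

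For 8/25 vs 2/25, the Wilson limits are 17.2% to 51.6% and 2.2% to 25.0%. In percentage points:
- lower = 24 − √[(32 − 17.2)² + (25.0 − 8)²] = 1.5
- upper = 24 + √[(51.6 − 32)² + (8 − 2.2)²] = 44.4

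Uncorrected chi-square for the same table: 50 × (8×23 − 17×2)² / (25×25×10×40) = 4.5, p = 0.034.

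| Assumed counts | Difference (95% interval), points | Chi-square p | Fisher p | Smallest expected count |
|---|---|---|---|---|
| 8/25 vs 2/25 | 24 (1.5 to 44.4) | 0.034 | 0.074 | 5 |
| 6/25 vs 2/25 | 16 (−5.1 to 36.3) | 0.123 | 0.247 | 4 |
| 8/25 vs 4/25 | 16 (−7.8 to 37.8) | 0.185 | 0.321 | 6 |

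- *Week 8 contrast smaller.* 8 vs 2 women ever report an event, and two of the eight do not report it again at Week 8. The difference falls from 24 to 16 points.
- *Week 8 contrast larger.* 8 vs 4 women ever report it, and two of the four do not report it again. The difference rises from 16 to 24 points.

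In both cases two women account for 2/25 = 8 points.

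**Step 4: small counts.** With equal arms of 25, the expected number reporting in each arm is (total reporting)/2. This is below 5 whenever fewer than 10 women in total report the event.

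**The case against.** The strongest reply is that no loss of events has been shown. The adverse-event form and the Operations Manual are not among the documents. If the Week 8 form asks about the whole treatment period and ET reports are counted, the literal rule and the cumulative rule should largely agree. This stands: what the text shows is a rule that can drop events, not one that is known to do so. The windows of other instruments do not settle it either way. The OAB-q asks how much the woman was "bothered by selected bladder symptoms during the previous week", while of the global improvement item F8 says "This is compared to pre- intervention (so there is no baseline value". Neither describes the adverse-event form.

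Second, the repeated pairing of Early Termination with Week 8 suggests that an ET visit takes the Week 8 place. A reader might infer that women who stop early are excluded from SA3; the documents do not support that. Women off drug are urged to keep attending, and the pairing points towards inclusion. What remains is that a visit description is not an analysis rule.

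Third, a reader might infer a bias in a known direction, for instance because dose adjustment changes active drug only in the mirabegron arm (E2.a). Nothing in the documents says how events persist or resolve in either arm, so no direction can be claimed.

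Finally, the earlier reports are still collected and could be tabulated later, and SA3 is a preliminary aim of a pilot. This limits the severity. It does not supply the missing definition.

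**Conclusion.** The point holds in limited form. As written, the only between-arm adverse-event analysis uses the Week 8 report, and nothing brings in the Week 2 and Week 4 reports or states that ET reports count. Events not reported again at Week 8 are left out if the rule is followed literally and the Week 8 form does not look back over the whole period. Size and direction are unknown. The 8-point shifts show only how sensitive a comparison of 25 with 25 is to two reports; they rest on assumed counts and are not estimates. The limitation of the chi-square test for uncommon events follows from the arm size alone. Severity is low to moderate: section K reports no power analysis, so no power claim is affected, but a stated aim lacks a defined outcome.

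**What to change.** Replace the SA3 sentence with a definition along these lines:

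- For each adverse event, the outcome is at least one report from first dose through Week 8 or Early Termination, using all scheduled reports (Week 2, Week 4, Week 8, ET), by assigned arm.
- Counts and risk differences with 95% intervals (for example Newcombe's) are given for each event. An exact test replaces chi-square where an expected count is below 5.
- The number of women with no report after first dose, and the number with incomplete follow-up, are shown by arm. The second number is needed because a woman whose only report is an event-free Week 2 call would otherwise pass as event-free through Week 8.
- Week 8 prevalence is given as a secondary result.

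The recall period of the adverse-event form should be stated in the same place.

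Cost: wording only, since E5 already schedules the reports and no visit or form is added. There is a trade-off: cumulative counts mix brief and lasting events, and women who leave early have fewer chances to report. The secondary Week 8 prevalence and the follow-up counts let the reader judge both. The rule should be fixed before treatment codes are broken.

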We propose a pilot study to assess the feasibility of enrolling ~50 community-dwelling, ambulatory women aged 65 years and older with urgency or mixed urgency predominate urinary incontinence into a randomized, controlled trial, to determine whether elderly women will adhere to an 8-week drug regimen and estimate the effect size necessary to show differences cognitive decline between Mirabegron and a standard anticholinergic therapy.

B. STUDY SYNOPSIS

Fifty community-dwelling women, ambulatory women with urgency or mixed urgency predominate urinary incontinence and at least 3 urgency incontinence episodes on a 3-day ~~screening diary, will be randomized to 8 weeks of Mirabegron (Myrbetriq) or tolterodine~~

tartrate (Detrol LA). The study will take place at the UCSF Women's Health Clinical Research Center.

C. SPECIFIC AIMS

The Specific Aims are to:

SA1: Assess the feasibility of enrolling and retaining women aged 65 years and older with urgency urinary incontinence in a randomized, controlled trial of an 8-week medication study.

SA2: To estimate preliminary differences in the effects of mirabegron compared to a standard anticholinergic therapy on cognitive function and calculate the standard deviation for: 1) a standard cognitive function battery, and 2) global patient perception of cognitive function.

SA3: To collect preliminary data on differences in change in physical function/mobility and other adverse events associated with Mirabegron vs. a standard anticholinergic therapy, such as dry mouth, constipation, vision, and falling.

SA4: Determine the differences in patient satisfaction between Mirabegron and a standard anticholinergic therapy in the treatment of urgency urinary incontinence.

SA5: To estimate preliminary differences in the efficacy of Mirabegron compared to a standard anticholinergic therapy on reducing urinary incontinence frequency, as assessed by validated 3-day voiding diary.

D. STUDY POPULATION

D1. Inclusion Criteria

Inclusion criteria reflect patients appropriate for treatment by primary care.

- Community-dwelling, ambulatory females \geq 65 years old

- Urgency or Mixed Urgency Predominate Urinary Incontinence (subject-reported) for ≥ 3 months prior to Screening (Visit 1)
- On a 3-day voiding diary, documentation of at least 3 urgency incontinence episodes with the number of urgency incontinence episodes greater than number of stress incontinence episodes

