- Urinary retention (post-void residual urine volume >150 cc measured by bladder scan at screening).

[figure not shown]
- Use of any electrostimulation, bladder training, or pelvic floor exercises (with certified incontinence practitioners) within 4 weeks of Screening.
- Use of mirabegron or tolterodine in the past 6 months.
- Has been treated within 4 weeks prior to Screening and/or is currently being treated with:
 - Any drug treatment for OAB
 - Any drugs with significant anticholinergic and antispasmodic effects (see exception for tricyclic antidepressants below)
- Has started treatment with or changed dose of tricyclic antidepressants or estrogens within 4 weeks prior to Screening.
- Intermittent use or unstable dose of diuretics. Treatment with diuretics initiated within 4 weeks prior to baseline and/or is not on a stable dose is not permitted.
- Treatment with potent CYP3A4 inhibitors, such as clarithromycin, ketoconazole, and itraconazole within 4 weeks prior to Screening.
- Administration of medications capable of inducing hepatic enzyme metabolism or transport (e.g., barbiturates, rifampicin, carbamazepine, phenytoin, primidone, or St. John's Wort) in the past 4 weeks.
- Administration of narrow therapeutic index drugs metabolized by CYP2D6, such as thioridazine, flecainide, and propafenone.
- Previously received any investigational drug within 30 days prior to trial entry.
- Alcohol and/or any other drug abuse in the opinion of the investigator.
- Participants who, in the opinion of the Investigator, have any medical (including known history of major hematological, renal, cardiovascular, or hepatic abnormalities) or psychological condition or social circumstances that would impair their ability to participate reliably in the trial, or those who may increase the risk to themselves or others by participating.
- Participants who, in the opinion of the investigator, are not likely to complete the trial for whatever reason.

Participants must meet all inclusion and exclusion criteria to be randomized to trial treatment.

E. STUDY DESIGN

Approximately 50 women with urgency or mixed urgency predominate urinary incontinence will be randomized in a 1-to-1 ratio to either mirabegron or tolterodine tartrate for 8 weeks.

E1. Study Overview

E2. Study Medication and Placebo

E2.a Dosing Regimen

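### Adverse events and the memory item are compared by significance tests, with no planned between-arm estimate or interval, although aims SA3 and SA2 ask for preliminary differences

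*Combined protocol and SAP*

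**What the plan says.** **Adverse events.** Aim SA3 (section C) reads "To collect preliminary data on differences in change in physical function/mobility and other adverse events", with examples "such as dry mouth, constipation, vision, and falling". Section L, under SA 3, gives one sentence of analysis: "Standard chi-square tests will be used to determine differences in report of adverse events at week 8". It mentions no per-arm proportions, risk difference or interval.

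**Memory item.** Aim SA2 (section C) lists two outcomes for which preliminary differences and a standard deviation are wanted: the cognitive battery and the patient's global perception of cognitive function. The analysis of the second appears in section L under the label SA 4. It consists of the number and proportion in each of five response categories, followed by a test: "Chi-square test for trend will be used to determine differences patient perception of cognitive change at week 8". Section L does not say whether the proportions are tabulated by arm. It names no effect measure, interval or SD for this item.

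**Other outcomes.** Under SA 2 and SA 5, section L uses ANCOVA to estimate differences and SDs for cognitive test scores, physical function and mobility scores, and incontinence frequency.

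**Size.** Section K: "We plan to study up to 50 women with approximately 25 randomized to Mirabegron", with a similar number on the comparator. It adds that "power analyses based on a sample size of 50 were not done for this proposal".

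**The concern.** The plan frames itself as estimation, and for that reason does not claim power. For these two outcomes, however, the between-arm comparison is a test meant to determine differences. A p-value from about 25 women per arm gives neither the size of a difference nor its uncertainty, so the stated analysis does not deliver what SA3 and the second half of SA2 ask for.

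The background section argues for the trial on comparative safety in older women, so adverse-event contrasts and perceived cognitive change are among the results a planner of a later trial would look for. If only test results are reported, a non-significant comparison leaves that planner unable to tell a small difference from a large one that was poorly measured.

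**Working it through.** **Inputs.** From the documents: about 25 per arm (section K), allocated 1:1 (section E). Assumed, because the documents state neither: two-sided 5% level, and all event counts and rates below. There is no power or precision calculation to reproduce; the only arithmetic in section K is 25 + 25 = 50, which agrees.

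**Step 1: aims against analyses.**

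| Outcome | Aim asks for | Section L plans | Missing |
|---|---|---|---|
| Cognitive battery | difference and SD (SA2) | ANCOVA difference and SD | nothing |
| Physical function and mobility | differences in change (SA3) | ANCOVA difference and SD | nothing |
| Adverse events | data on differences (SA3) | chi-square test | proportions, risk difference, interval |
| Memory item | difference and SD (SA2) | category proportions, trend test | between-arm effect, interval, SD |
| Incontinence frequency | difference (SA5) | ANCOVA difference and SD | nothing |

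**Step 2: what the planned test would show, and what an estimate would show.** Take 3/25 against 8/25.

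- Pearson chi-square = N(ad - bc)² / (product of the four margins) = 50 × (3×17 - 8×22)² / (25×25×11×39) = 50 × 15,625 / 268,125 = 2.91 on 1 df, p = 0.088.
- Risk difference = 0.32 - 0.12 = 0.20.
- Wilson 95% limits: 0.042 to 0.300 for 3/25, and 0.172 to 0.516 for 8/25.
- Newcombe lower limit = 0.20 - √[(0.32 - 0.172)² + (0.300 - 0.12)²] = 0.20 - 0.233 = -0.033.
- Newcombe upper limit = 0.20 + √[(0.516 - 0.32)² + (0.12 - 0.042)²] = 0.20 + 0.211 = 0.411.

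The test says not significant. The interval says anything from 3 points in one direction to 41 in the other. The same calculation for other illustrative splits:

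| Events per 25 | Pearson p | Risk difference (points) | Newcombe 95% CI (points) |
|---|---|---|---|
| 2 vs 5 | 0.22 | 12 | -8 to 32 |
| 3 vs 8 | 0.088 | 20 | -3 to 41 |
| 5 vs 10 | 0.12 | 20 | -5 to 42 |
| 0 vs 4 | 0.037 | 16 | -0.4 to 35 |

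The last row shows that a significant result is no more precise. Even no events in an arm of 25 is compatible with a true rate of up to 1 - 0.025^(1/25) = 13.7%.

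**Step 3: is the test itself at fault?** All four expected counts reach 5 only if at least 10 of the 50 women report the event (and at least 10 do not). If the true rate is the same in both arms, the chance of falling short is 97.5% at a 10% rate, 79% at 15%, 44% at 20% and 4% at 30%. Enumerating all 26 × 26 outcomes, however, the uncorrected Pearson test rejects a true null 2.0% of the time at a 5% rate, 4.9% at 10%, 5.5% at 20%, and at most 6.5% (at 50%). The trend test, simulated with 80% of women answering about the same, rejects 4.8% of the time. Sparse counts therefore do not materially inflate false positives.

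Fisher's test would cost power: for true rates of 10% and 30%, 45% (Pearson) falls to 30% (Fisher); for 20% and 40%, 35% falls to 23%.

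**The case against.** This is a feasibility pilot with no confirmatory hypothesis. Section K ties the planning of a larger trial to the battery SD and the potential effect size, and ANCOVA supplies estimates for the battery. Adverse-event differences are not named there as planning inputs. The memory item does get category proportions, and if these are tabulated by arm a crude difference follows. Investigators could also compute proportions and intervals later without being told to. All of this stands, and it keeps the point modest. It does not remove the mismatch: SA3 and SA2 name these differences as aims, and section L commits to no between-arm estimate for them.

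Three stronger readings are tempting, and the documents do not support them.

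- A reader might infer that chi-square tests on sparse counts are unreliable here. Step 3 does not bear this out: the Pearson test is conservative for rare events and only slightly liberal for common ones. The gap for 0 vs 4 (Pearson p = 0.037, Fisher p = 0.110) partly reflects Fisher's conservatism. How sparse the counts will be is also unknown, because no rates are given.
- A reader might fault the trial for low power on adverse events. Power is indeed low, but the plan openly makes no power claim, and no rewording of the analysis can recover it.
- A reader might conclude that the pilot yields no estimates at all, or that the memory item is only tested. Neither is so: the gap is limited to the between-arm comparison of these two outcomes.

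**Conclusion.** The point holds in a limited form. For adverse events the plan states a chi-square test and nothing else. For the memory item it states category proportions and a trend test, but no between-arm effect, interval or SD. Both fall short of the plan's own aims.

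The consequence is a loss of information, not an invalid test: at 25 per arm the unreported uncertainty would be roughly 37 to 48 points wide for splits such as 1 vs 4, 3 vs 8 or 5 vs 10. These widths rest on full follow-up of 25 per arm and on illustrative counts; with fewer evaluable women the intervals widen. The gap between aims and analyses rests on the text alone and needs no assumption about rates. It is worth correcting, but it does not threaten the feasibility aims or the ANCOVA outcomes.

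**What to change.** In section L, make estimation the primary analysis for these two outcomes.

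- **Adverse events:** for each event named in SA3, report n (%) per arm and the risk difference with a 95% CI by the Newcombe or Miettinen-Nurminen method.
- **Memory item:** report category counts by arm, the SD that SA2 asks for, and one prespecified between-arm effect with a 95% CI. This can be either the difference in the proportion reporting worse memory and thinking or the probability of a worse rating. Either avoids fitting an ordinal model to five categories with about 25 women per arm.
- **Tests:** keep the planned chi-square and trend p-values, labelled descriptive. A change to Fisher's exact test is not needed.

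The cost is a few sentences of SAP wording and a little more analysis work, with no new data, visits or participants. The intervals will look wide, which is an accurate picture of what 25 per arm can show.
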